10.3 Development of CNV During the Trial

If the Investigator suspects the development of CNV in the study eye, or if the subject has > 5 ETDRS letters of VA loss between the current visit and the immediate past visit where VA was assessed, the diagnosis must be assessed with fundus photography, FA and OCT and **confirmed by the Duke RC prior** to initiating anti-VEGF treatment in the study eye. The trigger for imaging studies should be the Investigator's suspicion of CNV. VA change alone does not constitute a requirement for imaging studies.

For patients who develop CNV in the study eye and the diagnosis is confirmed by the Duke RC during the trial, the study eye should be treated with either Lucentis® (ranibizumab), Eylea® (aflibercept), or Vabysmo® (faricimab) per their label.

If the Investigator plans to administer the anti-VEGF agent on the day of the diagnosis, the Duke RC will confirm the diagnosis within 1 hour after receiving the images. If the anti-VEGF agent and avacincaptad pegol are administered in the SE on the same day, avacincaptad pegol should be administered first, and the anti-VEGF administered second. The anti-VEGF agent may NOT be administered after the avacincaptad pegol injection until the IOP is ≤ 21 mmHg or within 5 mmHg of the baseline IOP on that day (i.e., the "baseline" IOP is the pre-injection IOP before the avacincaptad pegol administration on that day). If the IOP is **not** ≤ 21 mmHg or within 5 mmHg of the baseline IOP, the IOP should continue to be monitored until it is ≤ 21 mmHg or within 5 mmHg of the baseline IOP before proceeding to the anti-VEGF injection.

For the anti-VEGF agent administration, it is **mandatory** that, the same injection preparation and administration protocol specified for the avacincaptad pegol administration be followed by the ophthalmologist. Please refer to [Appendix 17.2](#) Intravitreal Administration Protocol; for example, the use of aseptic technique, sterile gloves, anesthesia, eye speculum, and povidone-iodine are required.

IVT injection is contraindicated in patients with active ocular or peri-ocular infections and in patients with active intraocular inflammation.

The subject will continue with the study treatment (avacincaptad pegol) as scheduled.

For patients who develop CNV in the fellow eye during the trial, the fellow eye should be treated with either Lucentis® (ranibizumab), Eylea® (aflibercept), or Vabysmo® (facimab) per their label, with no change to trial conduct regarding the study eye. **However, if the study eye is treated on the same day as the fellow eye, the study eye should be treated before the fellow eye.**

10.4 Withdrawal from Trial

Patients have the right to withdraw from the trial at any time for any reason. The Investigator (after consultation with the Sponsor) or Sponsor also have the right to withdraw patients from the trial in the event of concurrent illness, AEs (including pregnancy in female patients), treatment failure after a prescribed procedure, protocol violations, regulatory authority decision, cure, administrative or other reasons.

Final trial assessments as outlined in the Study Assessments Chart, [Section 3](#), should be performed on all patients who withdraw. Patients who withdraw due to an AE should be followed until resolution of the AE, or an adequate explanation for the event is obtained.

Patients who withdraw for any reason should have assessments performed according to the Early Withdrawal schedule.

10.5 Study Drug Discontinuation

In rare instances, it may be necessary for a subject to permanently discontinue study treatment before the planned study duration. If study treatment is permanently discontinued, the subject should, if at all possible, remain in the study to be evaluated for safety.

Subjects who discontinue study treatment or who decide they do not wish to participate in the study further should not be considered discontinued from the study unless they withdraw their consent and where possible, they should return for study visits and assessments according to the Study Assessments Chart, [Section 3](#).

10.6 Trial Discontinuation

The reason for a subject discontinuing from the trial will be recorded in the source documentation and CRF. A discontinuation occurs when an enrolled subject ceases participation in the trial, regardless of the circumstances, prior to completion of the protocol. The Investigator must determine the primary reason for discontinuation. A discontinuation must be reported immediately to the clinical monitor or his/her designated representative if it is due to an SAE (see [Section 12.3](#)). The final evaluation required by the protocol will be performed at the time of trial discontinuation. The Investigator will record the reason for trial discontinuation, provide or arrange for appropriate follow--up (if required) for such patients, and document the course of the subject's condition.

Premature termination of this clinical trial may occur because of a regulatory authority decision, change in opinion of the IRB/EC, or at the discretion of Astellas.

The trial will be considered completed when the last subject completes the final trial visit, and any repeat assessments associated with this visit have been documented and followed-up appropriately by the Investigator.

A subject is considered to have completed the study if the subject has completed the final trial visit.

11 STATISTICAL METHODS

The following summarizes the statistical methods that will be employed in this trial.

11.1 Study Endpoints

Primary endpoint:

- All AEs reported whether or not deemed related to the injection procedure or study drug

Secondary endpoints:

- Immunogenicity
- Pharmacokinetics

Exploratory Endpoints:

- Ophthalmic variables (BCVA, LLVA, IOP, and ophthalmic examination)

11.2 Determination of Sample Size and Statistical Rationale

The sample size is estimated based on the number of ISEE2008 subjects that completed the ISEE2008 Month 24 visit ("ISEE2008 completers") and the expected number of eligible ISEE2008 completers willing to participate in the ISEE2009 study.

11.3 Randomization and Masking Procedures

No randomization or masking procedures are necessary for this trial as it is an open-label trial and all eligible patients will be administered avacincaptad pegol 2 mg monthly.

11.4 Analytical Considerations

11.4.1 Safety Analysis

The safety analysis will be conducted on all patients who had at least one administration of study drug.

AEs will be summarized using Medical Dictionary for Regulatory Activities terms. The incidence and severity of AEs will be listed and grouped by body system.

Summary statistics (i.e., mean, median, standard deviation, minimum and maximum for continuous variables, counts and proportions for categorical variables) will be presented for all endpoints.

11.5 Immunogenicity and PK Analyses

Additional details regarding immunogenicity and pharmacokinetic data analyses will be provided in the statistical analysis plan (SAP) prior to database lock.

Immunogenicity: A patient's overall ADA status will be reported as follows: ADA-negative, ADA-positive, ADA-inconclusive and Unevaluable samples.

Pharmacokinetics: Individual patient concentration-time data will be listed and summarized descriptively in tabular format.

11.6 Interim Analyses

Interim analyses may be performed if deemed appropriate. Details (if applicable) will be described in the SAP.

12 ADVERSE EVENTS

12.1 Definition of Adverse Events

An AE is defined as follows: Any untoward medical occurrence in a patient or subject including unfavorable and unintended signs, symptoms or disease temporally associated with the use of a medicinal product and which does not necessarily have to have a causal relationship to this treatment.

AEs include illnesses with onset during the trial, or exacerbations of pre-existing illnesses. Exacerbation of pre-existing illness is defined as a significant increase in the severity of the illness as compared to the start of the trial and should be considered when a patient requires new or additional treatment for that illness. Lack of or insufficient clinical response or efficacy should not be recorded as an AE.

In addition, clinically significant changes in objective findings (e.g., laboratory, electrocardiogram, X-ray, physical examination) should also be considered as to whether they are AEs. The criteria for determining whether an objective finding should be reported as an AE are as follows:

1. Associated with accompanying symptoms; and/or
2. Requires medical/surgical intervention; and/or
3. Leads to a change in trial dosing or discontinuation from the trial, significant additional concomitant drug treatment or other therapy; and/or
4. Leads to any of the outcomes included in the definition of a SAE; and/or
5. Is considered to be an AE by the Investigator or Sponsor.

Any abnormal test result that is determined to be an error does not require reporting as an AE.

12.2 Assessment and Reporting of Adverse Events

AEs will be recorded starting after the first dose of study drug and continuing until 30 days after the last dose or until the last follow -up visit required by the protocol, whichever comes later. An AE that is ongoing at the last follow up trial visit is required to be followed up until the event resolves or stabilizes at a level acceptable to the Investigator and/or Sponsor. If the subject still presents with any treatment -related toxicity, the follow-up period will be extended until return to baseline status or until the condition has stabilized.

All AEs spontaneously reported, elicited, or observed by the Investigators will be recorded. The events will be recorded in the source documents and onto the AE pages of the CRF, including

date of onset and resolution, severity, relationship to trial treatment and determination of whether the event qualifies as a “serious” AE ([Section 12.3](#)).

Diagnostic and therapeutic non-invasive and invasive procedures, such as surgery, should not be reported as AEs. However, the medical condition for which the procedure was performed should be reported if it meets the definition of an AE. For example, an acute appendicitis that begins during the AE reporting period should be reported as the AE, and the resulting appendectomy should be recorded as treatment of the AE.

The Investigator will take all therapeutic measures necessary for resolution of the AE. Any medication necessary for treatment of the AE must be recorded in the subject’s source documents and on the appropriate pages of the subject’s CRF.

To assist with grading of AE severity, the following definitions are provided:

- Mild** = Aware of sign or symptom, but easily tolerated;
- Moderate** = Discomfort enough to cause interference with usual activity;
- Severe** = Incapacitating with inability to work or do usual activity;

AEs are assessed as “not related” or “related” to one of the following: (1) the IVT injection procedure (including eyelid speculum, anesthetic drops, mydriatic drops, antibiotic drops, povidone-iodine, subconjunctival injection of anesthetic, IVT injection of avacincaptad pegol or anti-VEGF) or (2) the study drug (avacincaptad pegol).

The adverse relationship will be assessed using the definitions below. The Investigator will choose either “not related”, or chose the most likely cause of the AE (i.e., only one of the relationships noted in the above paragraph may be chosen):

- Not Related** = There is not a reasonable possibility that the AE is related to the IVT injection procedure or to the study drug (avacincaptad pegol).
- Related** = There is a reasonable possibility that the AE is related to the IVT injection procedure or to the study drug (avacincaptad pegol).

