12.5 Assessment and Reporting of Serious Adverse Events

SAEs will be recorded starting after the first dose of study drug and continuing until 30 days after the last dose or until the last follow-up visit required by the protocol, whichever comes later. Any SAE occurring at any other time after completion of the trial must be promptly reported if a causal relationship to study drug is suspected.

If a SAE occurs, the Sponsor is to be notified within 24 hours of awareness of the event by the Investigator. In particular, if the SAE is fatal or life--threatening, notification to the Sponsor must be made regardless of the extent of available AE information. This timeframe also applies to additional new information (follow-up) on previously forwarded SAE reports.

**All Serious Adverse Events must be reported by the site
to the Sponsor or Designee within 24 hours.**

Refer to the “Safety Contact List” provided separately

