4.6.1 Adverse Events

All AEs will be coded in MedDRA. AE analysis will be based on the SAF.

A treatment-emergent adverse event (TEAE) is defined as an AE starting after the first administration of the study drug in this study until 30 days after the last administration of the study drug or until the last follow-up visit required by the protocol, whichever comes later.

An overview table to report the number and percentage of participants and number of events will include but not limited to the following:

- TEAEs,
- Drug related TEAEs,
- Serious TEAEs,
- Serious drug related TEAEs,
- TEAEs leading to withdrawal of study drug,
- Drug-related TEAEs leading to withdrawal of study drug,
- Severe TEAEs,
- TEAEs leading to death,
- Drug related TEAEs leading to death,
- Deaths.

An additional overview of TEAEs will be provided which displays the overall summary of TEAEs by three categories (SE, FE, and non-ocular).

The number and percentage of participants with TEAEs, as classified by SOC and PT will be summarized for each cohort. Summaries will be provided for the following:

- TEAEs,
- TEAEs with frequency of $\geq 5\%$ in any cohort,
- TEAEs with frequency of $\geq 2\%$ in any cohort,
- Non-serious TEAEs with frequency of $\geq 5\%$ in any cohort,
- Study drug related TEAEs,

- Injection procedure related TEAEs,
- Serious TEAEs,
- Serious study drug related TEAEs,
- Serious injection procedure related TEAEs,
- TEAEs leading to withdrawal of study drug,
- Study drug related TEAEs leading to withdrawal of study drug,
- Injection procedure related TEAEs leading to withdrawal of study drug,
- TEAEs leading to death,
- Study drug related TEAEs leading to death,
- Injection procedure related TEAEs leading to death.

Ocular TEAEs have been defined as TEAEs linked to the “Eye Disorders” SOC or the “Intraocular Pressure Increased” PT.

The number and percentage of participants with ocular TEAEs or non-ocular TEAEs, as classified by SOC and PT, will be summarized for each cohort. Summaries will be provided for those including but not limited to the following:

- Ocular TEAEs by SE and FE,
- Ocular TEAEs with frequency of $\geq 2\%$ in any cohort (by PT),
- Non-ocular TEAEs with frequency of $\geq 2\%$ in any cohort (by PT),
- Study drug related Ocular TEAEs (SE),
- Injection procedure related Ocular TEAEs (SE),
- TEAEs with high level term of cataract conditions by SE and FE,
- Serious ocular TEAEs (SE),
- Serious study drug related ocular TEAEs (SE),

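### Recording only the single most likely cause makes drug-related adverse event counts equal to or lower than the protocol's own definition of related implies

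*Protocol*

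**What the plan says.** Protocol 12.2 sets the test for a related event: "There is a reasonable possibility that the AE is related to the IVT injection procedure or to the study drug". One definition serves both causes, and it does not treat them as alternatives.

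The same section then sets the recording rule. The investigator either enters not related or must "chose the most likely cause of the AE", and "only one of the relationships noted in the above paragraph may be chosen". The procedure option lists the steps around the injection and ends by naming the injections themselves, next to the competing option: "IVT injection of avacincaptad pegol or anti-VEGF) or (2) the study drug (avacincaptad pegol".

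SAP 4.6.1 uses the recorded attribution in three places:

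- The overview table has rows such as "Serious drug related TEAEs", plus drug-related rows for all TEAEs, withdrawal and death. The term drug related is not defined, and no procedure-related or either-cause row is listed.
- The SOC and PT tables give "Study drug related TEAEs" and, separately, injection-procedure-related TEAEs. Both are repeated for serious events, withdrawal and death, and both appear in the severity and study-eye ocular summaries. No table combining the two is listed.
- The AE listing shows causality for drug and for procedure.

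Protocol 12.5 has one reporting rule tied to the drug. It covers SAEs arising after the trial is completed, which "must be promptly reported if a causal relationship to study drug is suspected".

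**The concern.** The definition asks whether a cause is reasonably possible. The recording rule asks which cause is most likely. The second test is stricter, and it is the one that reaches the database. A reader of a drug-related table will assume it follows the written definition, when it counts only events for which the drug was the leading suspect.

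The two options are hard to separate because giving the drug is part of the procedure option. Protocol 12.3 also says that the AESIs were chosen for procedure risks and for potential risks of the drug's mechanism, so the protocol expects both kinds of cause. The form cannot record both for one event.

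Attribution also carries more weight here than in the parent trial, which had a sham arm. In this extension everyone receives avacincaptad pegol. With no concurrent control, the investigator's judgement is the only separation of drug from procedure within the trial.

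**Working it through.** The documents give no figure on this point, so there is none to reproduce. The check has three steps.

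**1. Which counts move, and in which direction.** Sort related events by which causes are reasonably possible: D0 drug only, P0 procedure only, B both. Let q be the share of B recorded under procedure as the likelier cause.

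| Count | By the 12.2 definition | As recorded | Shortfall |
|---|---|---|---|
| Drug related | D0 + B | D0 + B(1 − q) | B × q |
| Procedure related | P0 + B | P0 + B × q | B(1 − q) |
| Either cause | D0 + P0 + B | D0 + P0 + B | 0 |

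Because q lies between 0 and 1, the drug-related shortfall lies between 0 and B and is never negative. The procedure count loses whatever the drug count keeps. The either-cause count is complete, because every related event carries one of the two codes.

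**2. Whether the planned tables already give the either-cause count.** At event level it is the sum of the two recorded counts. The SOC and PT tables count participants, and a participant with one event of each kind appears in both. From those tables a reader learns only that the either-cause number is at least the larger of the two counts and at most their sum. The exact number has to be programmed from the records. The procedure table also cannot stand in for the missing drug-possible events, because the procedure option covers anti-VEGF injections too.

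**3. Illustration of scale.** Inputs from the documents: planned enrolment of about 280 (Protocol 8.1), and the 12-month rates in Protocol 4.6 of 13% for conjunctival hemorrhage, 9% for increased IOP and 7% for CNV. Assumptions: these rates carry over, there is one event per participant, and every such event has a reasonable possibility of both causes. The value of q is unknown, so its full range is shown. B = 280 × rate, and the recorded drug-related count is B(1 − q).

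| Event | B | q = 0 | 0.25 | 0.5 | 0.75 | 1 |
|---|---|---|---|---|---|---|
| Conjunctival hemorrhage | 280 × 0.13 = 36.4 | 36.4 | 27.3 | 18.2 | 9.1 | 0 |
| Increased IOP | 280 × 0.09 = 25.2 | 25.2 | 18.9 | 12.6 | 6.3 | 0 |
| CNV | 280 × 0.07 = 19.6 | 19.6 | 14.7 | 9.8 | 4.9 | 0 |

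The assumption that all these events have both causes is deliberately extreme. The table shows that the recorded count depends wholly on q. It is not a forecast.

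**The case against.** The strongest reply is that little is lost. An event recorded under procedure moves to a parallel table, since SAP 4.6.1 gives procedure-related summaries overall and for serious, withdrawal, death, severity and study-eye ocular events, and the listing shows causality. The overview is open to further rows. Because its drug-related term is undefined, it is not certain that procedure events are excluded from it. No hypothesis is tested. This is fair and limits the consequence. It does not remove the mismatch between definition and recorded variable, and the undefined term is itself part of the problem.

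Four stronger readings are tempting, and the documents do not support them:

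- *The primary endpoint is biased.* Protocol 11.1 defines it as all AEs regardless of relationship, so only the relatedness summaries are affected.
- *AESI counts suffer most.* SAP 4.6.2 tabulates AESIs by category and cohort without a causality split, so an AESI attributed to the procedure is still counted.
- *Safety reports will be missed.* During the study, all SAEs go to the sponsor within 24 hours (12.5) and study-eye AESIs follow the same route (12.3), with no causality condition. The post-trial rule in 12.5 turns on suspicion of the drug and does not refer to the recorded choice. A missed report there is possible but is not a stated consequence. Sponsor expedited reporting is left to local legislation (13.5), so no effect on it can be shown.
- *The loss can be put at a given percentage.* If 30% to 60% of drug-possible events were also procedure-possible, and 50% to 90% of those were recorded as procedure, the loss would be 0.30 × 0.50 = 15% to 0.60 × 0.90 = 54%. None of those inputs comes from the documents.

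**Conclusion.** The point holds as a mismatch between the definition of related and the variable collected. It affects the study-drug-related and procedure-related summaries in SAP 4.6.1. For drug-related counts the direction is certain: equal to or lower than the definition implies. The size is unknown, from none to all of the dual-cause events, and nothing in the documents narrows it.

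At event level, the number meeting the definition for drug lies between the recorded drug-related count and the either-cause count. This assumes that events entered as not related truly have no reasonable possibility of either cause. Reporting both counts would therefore bracket the figure the definition calls for. The conclusion rests on the wording of 12.2, because the CRF itself is not among the documents.

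**What to change.** **In SAP 4.6.1, using data already recorded:**

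1. Define drug related, and state whether procedure-related events are included.
2. Add two rows to the overview: *related to study drug or injection procedure* and *injection procedure related*. Count each participant once per row.
3. Footnote every drug-related table to say that the term means the drug was judged the most likely single cause.

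**Where the CRF can still change:** replace the single choice in Protocol 12.2 with two yes/no items, one for the study drug and one for the injection procedure, with both allowed. Count an event as drug related whenever the drug item is yes.

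**Cost.** The SAP change is two table rows, a definition and a footnote. The CRF change needs new protocol and form wording. The related counts would look somewhat less favourable. If the form changes during the trial, events assessed under the old and new rules must be flagged so that the two kinds of judgement are not pooled without notice.

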12.3 Definition of AESIs

The selection of adverse events of special interest (AESIs) are based on medical review of avacincaptad pegol AEs throughout the development program and the post-marketing environment. These include identified risks for an IVT injection procedure and potential risks for avacincaptad pegol mechanism of action, considering the frequency, seriousness, and medical plausibility of events.

The AESIs will include the following:

- Endophthalmitis
- Ischemic optic neuropathy
- Intraocular inflammation; any case of uveitis, retinal vasculitis or retinal occlusive vasculitis
- IOP \geq 30 mmHg at 30 minutes post injection deemed clinically significant by the Investigator
- Transient loss of light perception immediately after injection
- Elevation of IOP post-injection requiring surgical/procedural intervention (i.e., paracentesis; for instruction regarding paracentesis refer to [Appendix 17.2](#))
- BCVA decrease \geq 30 letters from ISEE2009 Month 1 Visit
- CNV (exudative or nonexudative)

AEs, as defined in [Section 12.1](#), should be reported as per [Section 12.2](#).

An AESI, as defined in this [Section 12.3](#), shall be reported if affecting the study eye. When an AESI occurs, the Investigator will fill out a standardized questionnaire to report the designated event in the same expedited manner as SAEs ([Section 12.5](#)).

Adverse events of CNV, endophthalmitis and intraocular inflammation occurring in the fellow eye, while not considered an AESI per protocol, shall be entered in the CRF as expeditiously as possible (i.e., within 24 hours of event).

